## 10.5 Determination of Causality

The investigator is required to provide an assessment of relationship of AEs and SAEs to the investigational product. A number of factors should be considered in making this assessment including:

- Alternative possible causes of the AE, including the subject's underlying disease or comorbid conditions, other drugs, other host, and environmental factors
- The temporal sequence between the exposure to investigational product and the AE
- Whether the clinical or laboratory manifestations of the AE are consistent with known actions or previously reported toxicity of the investigational product or similar drugs
- Whether the AE resolved or improved with decreasing the dose or stopping the investigational product (i.e., dechallenge); or recurred or worsened with re-exposure to the drug (i.e., rechallenge).

Relationship assessments that indicate “*Not Related*” to investigational product:

- None: The event is related to an etiology other than the investigational product (the alternative etiology must be documented in the study subject's medical record and/or SAE form).
- Unlikely or Remote: The event is unlikely to be related to the investigational product and likely to be related to factors other than investigational product.

Relationship assessments that indicate “*Related*” to investigational product:

- Possible: There is an association between the event and the administration of the investigational product and there is a plausible mechanism for the event to be related to investigational product; but there may also be alternative etiology, such as characteristics of the subject's clinical status or underlying disease.
- Probable: There is an association between the event and the administration of investigational product, a plausible mechanism for the event to be related to the investigational product and the event could not be reasonably explained by known characteristics of the subject's clinical status or an alternative etiology is not apparent.
- Definite: There is an association between the event and the administration of investigational product, a plausible mechanism for the event to be related to the investigational product and causes other than the investigational product have been ruled out and/or the event re-appeared on re-exposure to the investigational product.

For AEs that occur prior to the administration of investigational product, an assessment of protocol relatedness must be made. AEs may occur as a result of procedures required during the screening process (e.g., blood collection, washout of an existing medication) prior to the initial administration of investigational product. For AEs that occur before administration of investigational product, only those that are assessed by the investigator as protocol-related should be reported to the Sponsor. The following guidelines should be used by investigators to assess the relationship of an AE to a protocol-required procedure:

- Protocol related: The event occurred due to a procedure/intervention that was described in the protocol for which there is no alternative etiology present in the subject's medical record.
- Not protocol related: The event is related to an etiology other than the study procedure (the alternative etiology must be documented in the study subject's medical record).

## 10.6 Documenting Adverse Events

All AEs (including SAEs) are to be accurately recorded on the Adverse Event page of the subject's electronic CRF from the time the subject signs the informed consent through the Follow-up Period. Each event will be assessed for serious criteria, severity, and causality (see [Section 10.5](#)). The date of onset, as well as the duration of the event will be recorded. In addition, treatments provided to the subject, actions taken with the investigational product, and the outcome of the AE will also be noted.

## 10.7 Reporting Serious Adverse Events

### Time Frame for Reporting

All SAEs must be reported to the Sponsor or Sponsor designee within 24 hours of awareness, regardless of initiation of new anticancer therapy including the following:

- Any death or SAE experienced by the subject from the signing of informed consent to 30 days after the last dose of investigational product, regardless of relationship to investigational product.
- Any death or SAE that the Investigator becomes aware of, and believes to be investigational product related, that occurs more than 30 days after the subject last received investigational product.

**All and SAEs must be reported to the following fax line within 24 hours of awareness:**

[REDACTED]

Additional data concerning the SAE (eg diagnostic test reports, hospital summaries, etc.) must be promptly reported (within 24 hours of receipt) to the Sponsor or Sponsor's designee, until resolution of the SAE. Should the FDA or National Regulatory Authorities require that the Sponsor submit additional data on the event, the investigator will be asked to provide those data to the Sponsor in a timely fashion.

### Information to be provided by the Investigator

Within 24 hours of becoming aware of the SAE or subject death, the investigator must notify the Sponsor or designee and transmit information to the Sponsor or designee. Information (initial and follow-up) should be provided on an electronic and/or paper SAE Report form signed and

dated by the investigator. The SAE Report form and copies of source documents (with subject identifiers redacted) will be transmitted by fax. A hospital discharge summary should be provided if the subject was hospitalized. An SAE report will be considered final once all relevant information has been received and reviewed by the Sponsor.

The SAE Report form is provided in the investigator study files. Please refer to the investigator study files for instructions on how to complete this form. The investigator will provide all of the following information related to the event:

- Investigator identification
- Subject identification (e.g., subject number, initials, sex, age or date of birth)
- Information regarding investigational product administration (e.g. start/stop date, dose, and frequency)
- Cycle and day of SAE occurrence documentation on SAE report forms
- Description of event
- Action taken with the investigational product in relation to the SAE
- Outcome of the SAE

In addition to the above information, the investigator must provide, for each event term, an assessment of:

- Severity/intensity
- Relationship to the investigational product (causality assessment)

## **10.8 Sponsor and Investigator Responsibility for Reporting Adverse Events**

All AEs and SAEs will be reported to regulatory authorities, IRBs/IECs, and investigators in accordance with all applicable global laws and regulations. The investigator must submit all Safety Letters received from the Sponsor to his/her IRB/IEC per agreements and local requirements. The investigator must keep copies of all safety reports/letters, including correspondence with ZIOPHARM and the IRB/IEC, in the study file.

## **10.9 Follow-up Information for Adverse Events**

Appropriate diagnostic tests should be performed and therapeutic measures, as medically indicated, per the investigator, should be instituted. Appropriate consultation and follow-up evaluations should be carried out until the event has resolved, stabilized, returned to baseline, or is otherwise explained by the investigator.

### **Required Follow-up for Adverse Events**

All AEs and SAEs will be collected from the signing of the ICF through Week 6. After Week 6, only SAEs suspected of being related to investigational product will be collected. Follow up information for ongoing SAEs will be requested by the Sponsor until one of the following occurs:

- The event resolves
- The event returns to baseline, if a baseline value is available
- The event stabilizes (following consultation and agreement by the medical monitor)
- The event can be attributed to factors other than the investigational product or other than study procedure

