#### Efficacy Assessments

Tumor response will use RECIST v 1.1 (see Section 9 of the main protocol). Injected and non-injected lesions will be assessed and recorded separately. Up to 5 measureable lesions may be selected and designated as target lesions. One measurable lesion will be injected and will be consequently designated a non-target lesion. Target lesions will be used to evaluate the systemic effect of Ad-RTS-hIL-12, as defined by RECIST v1.1. Additional non-injected, non-target lesions also may be followed, according RECIST v1.1. Target and non-target lesions will be assessed by CT at 6 weeks and 12 weeks after the start of Ad-RTS-hIL-12 immunotherapy. Tumor response will also be assessed by Immune-Related Response Criteria (irRC) ([Wolchok et al, 2009](#)). The imaging method used for the week 6 and week 12 assessments of response must be the same as that used for the pre-study assessments. The tumor assessment at 12 weeks after the start of Ad-RTS-hIL-12 immunotherapy will be compared with the pre-study tumor assessment when SD or PR was achieved.

Biologic/immunologic assessments will be performed using blood samples obtained at screening, days 1, 3, 8, and weeks 6 and 12. Tumor biopsies will be obtained by interventional radiology prior to the intratumoral vector injection and again at 6 weeks.

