- q. If radiographic PD is recorded at 6 weeks, PD must be confirmed 4 weeks later. In cases of slow tumor growth, the investigator may wait until confirmation of the PD at 12 weeks to resume chemotherapy. In cases of unequivocal progression, the investigator may resume chemotherapy prior to 12 weeks.
- r. Subjects who have SD or better at Week 12 will continue into the long-term follow-up period where imaging should continue per the schedule until a radiographic response of PD is confirmed.
- s. Biopsy on Day 1 is to be taken 3 hours  $\pm$  3 hours after administration of veledimex and prior to injection of Ad-RTS-hIL-12.
- t. After Week 6, only SAEs suspected of being related to investigational product will be collected.
- u. The follow-up visits can be performed within  $\pm$  1 week.

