#### **8.3.1.6      Monitoring of Adverse Events**

Monitoring and recording of AEs and SAEs will be conducted throughout the study. AEs and SAEs from the signing of informed consent until the end of week 6 will be collected and entered into the case report forms (CRFs). After Week 6, only SAEs suspected of being related to Ad-RTS-hIL12 immunotherapy will be collected.

Adverse events will be recorded on the CRFs using NCI CTCAE v.4.03 criteria. MedDRA will be used for evaluating AEs. Definitions, documentation, and reporting procedures for adverse events are described in detail in [Section 10](#).

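### The protocol gives conflicting AE/SAE collection windows; if the Week 6 rule is followed, a later serious complication of the Week 6 biopsy judged unrelated to product is not collected

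*Protocol*

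**What the plan says.** Three current places in the protocol state a Week 6 rule.

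- Section 10.9 collects all AEs and SAEs through Week 6, then: "After Week 6, only SAEs suspected of being related to investigational product will be collected".
- Section 8.3.1.6 has the same cut-off: "After Week 6, only SAEs suspected of being related to Ad-RTS-hIL12 immunotherapy will be collected".
- Footnote t of the Schedule of Study Procedures repeats the rule.

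Other current text sets a longer or wider scope.

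- The synopsis (Safety Assessments) has all AEs and SAEs collected from consent to the end of Week 12.
- Section 10.6 has all of them recorded through follow-up.
- The opening sentence of 8.3.1.6 has monitoring and recording run for the whole study.
- Section 8.4.9 lists adverse events among the Week 12 assessments.
- The lead sentence of 10.7 requires every SAE to be reported within 24 hours.

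The biopsy falls at the cut-off. The synopsis (Efficacy Assessments) says: "Tumor biopsies will be obtained by interventional radiology prior to the intratumoral vector injection and again at 6 weeks". Section 8.4.8 lists it at the Week 6 visit, and footnote u allows a margin of 1 week either side: "The follow-up visits can be performed within" that margin.

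On causality, Section 10.5 addresses study procedures only before dosing: "For AEs that occur prior to the administration of investigational product, an assessment of protocol relatedness must be made".

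**The concern.** An invasive research procedure is scheduled at the point where one version of the collection rule stops taking events regardless of cause. From then on, the only filter is relatedness to the investigational product. A complication caused purely by the biopsy is correctly classed as not related to product, so the Week 6 rule screens it out. No provision in that rule brings procedure-related harms back in.

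The text that would collect such an event sits elsewhere and disagrees with the rule. Site staff working from the Schedule and Section 10.9 would therefore collect a different set of events from staff working from the synopsis and Section 10.6. Safety and tolerability is the primary objective, so the collection window should not depend on which page is read. What is at stake is whether a serious harm of a protocol-required procedure reaches the safety record.

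**Working it through.** The protocol gives no figure of its own to reproduce. The check compares the rules and counts days.

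**Inputs**
- Last veledimex dose: Day 7 (Section 6.2; Schedule footnote j).
- Biopsy: Week 6 visit, plus or minus 1 week (Section 8.4.8; footnote u).
- Subjects who could have the Week 6 biopsy: at most 40 (Section 4.3).
- Assumed day numbers: Week 6 = 6 × 7 = Day 42; end of Week 12 = 12 × 7 = Day 84. The biopsy window is then 42 ± 7, or Day 35 to Day 49.

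**Step 1: does 10.7 fill the gap?** It lists two classes of SAE.
- The first is "Any death or SAE experienced by the subject from the signing of informed consent to 30 days after the last dose of investigational product", whatever the cause. It ends at Day 7 + 30 = Day 37, which is 42 − 37 = 5 days before an on-time biopsy. After a Day 35 biopsy it leaves 37 − 35 = 2 days.
- The second covers later events: "Any death or SAE that the Investigator becomes aware of, and believes to be investigational product related". It has the same product filter as the Week 6 rule.

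Neither item clearly takes in a late biopsy complication. The lead sentence could, if the two items are read as examples only.

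**Step 2: does 10.5 bring the event in?** Its procedure-relatedness assessment applies only before dosing, so it does not reach Week 6. Its category of possible relatedness does help. It applies when "there is a plausible mechanism for the event to be related to investigational product", even if another cause may exist. An event given that label counts as product-related and is collected. The gap is therefore limited to events judged unlikely or not at all related to product.

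**Step 3: all-cause collection days left after the biopsy.** Days left = max(0, cut-off day − biopsy day). The Week 6 rule does not fix its cut-off exactly, so three readings are shown beside the synopsis.

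| Biopsy day | Cut-off Day 42 | Cut-off at the visit | Cut-off at close of visit window, Day 49 | Synopsis, Day 84 |
|---|---|---|---|---|
| 35 | 7 | 0 | 14 | 49 |
| 42 | 0 | 0 | 7 | 42 |
| 49 | 0 | 0 | 0 | 35 |

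For an on-time biopsy the Week 6 rule leaves 0 to 7 days, against 42 under the synopsis.

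**Step 4: does a formal decision rest on these events?** The toxicity stopping rule counts product-related, treatment-refractory Grade 3 or 4 events within 21 days of starting therapy (synopsis; Sections 3.1 and 12.4.2). A biopsy at Day 35 or later is outside that period, and an unrelated event would not count in any case.

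**The case against.** The strongest reply is that the loss occurs on only one reading. The synopsis, Section 10.6, the opening of 8.3.1.6, the Week 12 visit list and the lead sentence of 10.7 can each be read to capture the event. This stands. A reader might infer that the protocol definitely discards late biopsy complications. The documents do not support that: they establish a contradiction between windows, and the loss depends on the Week 6 rule being the one followed. That is plausible, since the rule appears in three current sections. The Amendment 2 summary, used here only as evidence of intent, shows Section 10.9 being set to Week 6 and the rule being copied into the Schedule. But the same amendment left the synopsis at Week 12, so the point remains open.

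A reader might also infer that no all-cause collection remains after the biopsy on any reading. That is too strong: if the cut-off is the close of the visit window, an on-time biopsy leaves 7 days.

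A third inference is that the 12-week primary endpoint is compromised by the missing biopsy events. The link is weak. Sections 3.1 and 12.3.1 refer to Section 12.4.2, where the only Grade 3/4 criterion concerns related, treatment-refractory events. A biopsy complication judged unrelated would not meet it, whether collected or not.

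It can also be said that the affected class is small, that the sponsor chose the Week 6 rule deliberately, and that local IRB reporting duties (Section 13.6) may still apply. The class is indeed small. A deliberate choice of Week 6 does not explain why the synopsis and Section 10.6 say otherwise, and IRB reporting does not put an event in the study's safety data.

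**Conclusion.** The point holds as an internal contradiction with one identifiable consequence. Under the Week 6 rule, an event is not collected if it is a serious complication of the Week 6 biopsy, starts after the cut-off, and is judged not even possibly related to product. Under the synopsis it is collected if it starts by the end of Week 12.

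The day counts rest on taking Week 6 as Day 42 and the end of Week 12 as Day 84. The protocol gives no biopsy complication rate, so no expected count is offered; with at most 40 biopsies and so narrow a class, few events are likely. The result is a less complete safety record. The stopping boundaries are unaffected. This is worth correcting because it is cheap, but it does not threaten the trial's conclusions.

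**What to change.** 1. In 8.3.1.6, 10.9 and footnote t, set collection of all AEs and SAEs to the end of Week 12, matching the synopsis, and state the same end point in 10.6.
2. After Week 12, collect SAEs suspected of being related to the investigational product or to a protocol-required procedure. Put the same wording in the second item of 10.7. Leave the existing open-ended collection of product-related SAEs without an end date.
3. In 10.5, extend the protocol-relatedness assessment to events after dosing.

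The first change does most of the work, because it gives 35 to 49 days of all-cause collection after the biopsy. The second covers anything later, and the third lets a procedure harm be labelled as one. The conflict should not be resolved by narrowing the synopsis and 10.6 to Week 6. That would also leave out non-serious Grade 3 or higher events between Weeks 6 and 12, inside the 12 weeks the primary endpoint covers.

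The cost is protocol wording, one extra causality field on the AE form, and about 6 more weeks of AE recording per subject. The SAE count may rise slightly. No visit or procedure is added, since Section 8.4.9 already lists adverse events at Week 12.

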## 10.10 Pregnancy

Subjects who become pregnant during the study should immediately discontinue treatment. The Sponsor must be immediately notified.

An initial Pregnancy Report Form and a Pregnancy Outcome Form are to be completed by the investigator or designee. The Pregnancy Report form and the completion guidelines will be provided in the investigator study files. Please refer to the investigator study files for details on how to complete these forms.

## 10.11 Overdose

Investigational product overdose of study subject, with or without associated AEs/SAEs, should be reported within 24 hours of awareness to Sponsor [REDACTED]

[REDACTED] All AEs and SAEs as a result of overdose should be reported as described previously in [Section 10.6](#) and [Section 10.7](#), respectively.

# 11 BIOLOGIC AND IMMUNE RESPONSE ASSESSMENTS

## 11.1 Blood Cytokine and Immune Function Assessments from Blood

Soluble factors, such as cytokines, chemokines, soluble receptors, and antibodies to tumor antigens will be characterized and quantified by immunoassays in blood (serum or plasma). Analyses may include, but are not necessarily limited to blood IL-12, IL-10, and IFN- $\gamma$ . The proportion of specific lymphocyte subsets and expression levels of T cell co-stimulatory markers in peripheral blood mononuclear cell (PBMC) preparations will be quantified by flow cytometry. Analyses may include, but not necessarily be limited to, the proportion of T, B, and NK cells, proportion of memory and effector T cell subsets, and expression levels of PD-1, PDL1, ICOS, and Ki67.

## 11.2 Cytokine and Immunologic Markers Assessment from Tumor Tissue

Cytokines and immunologic markers will be examined in core biopsy (punch or FNA biopsy accepted in the absence of the core biopsy) taken on day 1 and at week 6. Biopsies will be evaluated by immunocytochemistry for evidence of tumor infiltration by effector cells such as T cells and their subsets, as well as immune suppressor elements, such as T-regulatory cells and myeloid-derived suppressor cells, and other immunological markers. Antibodies to be used in the immunocytochemistry analysis may include, but are not limited to those against cluster of differentiation (CD) antigens CD3, CD4, CD8, CD25, FOX-P3, and CD56, and CD45RO.

## 12 STATISTICAL METHODS

### 12.1 Populations for Analysis

The following subject populations will be evaluated and used for presentation and analysis of the data:

- The safety population will comprise all subjects who have received either the injection of Ad-RTS-hIL-12 or any doses of veledimex
- The veledimex-treated population will comprise subjects who have received the injection of Ad-RTS-hIL-12 and at least one dose of veledimex
- The veledimex-evaluable population will comprise subjects who have received the injection of Ad-RTS-hIL-12 and all 7 doses of veledimex

### 12.2 Sample Size and Power Calculations

A maximum of 40 patients will be treated. This patient population will be heterogeneous and as such, it is difficult to define a threshold for a clear null and alternative hypothesis. This sample size will allow us to estimate an overall progression rate at 12 weeks with a maximum 95% exact confidence interval half-width of 0.16. This is based on an exact binomial calculation and is an estimate. However, analysis of progression-free survival will be conducted using Kaplan-Meier methods.

### 12.3 Endpoints

#### 12.3.1 *Primary Endpoint*

- To evaluate the safety and tolerability of one cycle of Ad-RTS-hIL-12 immunotherapy a) following a first-, second-, or third-line standard treatment in HER2-negative (HER2-) subjects, or b) together with a first-, second-, or third-line anti-HER2 antibody therapy in HER2-positive (HER2+) subjects as defined by section 12.4.2.

#### 12.3.2 *Secondary Endpoints*

- To estimate the progression rate at 12 weeks after the start of one cycle of Ad-RTS-hIL-12 immunotherapy.
- To evaluate the overall response rate (ORR), defined as the rate of complete response (CR) plus the rate of PR at 12 weeks following the start of Ad-RTS-hIL-12 immunotherapy.
- To evaluate the disease control rate (DCR), defined as the proportion of subjects who have a CR, PR, or SD at 12-weeks following the start of one cycle of Ad-RTS-hIL-12 immunotherapy
- To evaluate the number of subjects whose baseline tumor status (SD or PR) improves to PR or better at 12 weeks following the start of Ad-RTS-hIL-12 immunotherapy
- To compare radiographic responses by irRC with conventional reporting by RECIST

- To explore the impact of treatment on tumor and serum immune biomarkers

